## Sample Size and Statistical Analysis

### Sample Size

The primary endpoint is the ARAT, the MCID for which is 5.7 points. This study is powered for the Aim 1 analyses, which will compare [1] patients receiving TR (i.e., combining TR+Sinemet with TR+placebo) to [2] patients receiving UC. Based on a randomization distribution of 3:3:2 (TR+Sinemet, TR+placebo, UC), and using a 2-sided alpha of 0.05, this study will have 80% power to detect a mean difference between groups of 5.7 points in the change in ARAT-time, assuming a SD of 7.4 points, with a total of 72 patients: 27 in TR+Sinemet, 27 in TR+placebo, and 18 in UC.

The study is funded to enroll 72 patients. Subject dropout may be as high as 20%, and so when possible additional patients may be enrolled.

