## Assessments

*Several standardized assessments will be conducted during this in-person visit:*

- FMA-UE
- BBT
- ARAT
- NHPT
- mRS
- SIS-hand and ADL subsections
- In addition, the patient will be asked about interval medical history and AEs

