### Statistical Analysis

We will present descriptive statistics by group for the important covariates including age, site, time from stroke to randomization, MEP status, and hours of outside rehabilitation. We will also report compliance, defined as the percentage of the 36 sessions during which patients complete more than half ( $\geq 36$  min) of assigned activities. For all analyses, data not normally distributed will be appropriately transformed.

Primary efficacy analysis will use the Intent-To-Treat population, consisting of all randomized subjects and multiple imputation for missing data. Secondary analysis will examine the Per-Protocol population, defined as all subjects with complete data who complete  $\geq 36$  minutes of assigned activities on  $\geq 30$  of the 36 therapy sessions over no more than 8 weeks. Analyses will be performed using SAS and R software.

Logistic regression will be used to create a propensity score for treatment group using age, time from stroke to randomization, and total hours of outside rehabilitation therapy from Visit 1 to Visit 4 (or Visit 3 when change is to visit 3). Inverse weights based on this score will be used in secondary analyses to compute adjusted change distributions and corresponding p values. The primary analyses will be based on the inverse propensity score weighted (adjusted) change from base. The corresponding unadjusted changes will also be reported as a secondary analysis. Since this is a randomized trial, we expected the primary propensity adjusted and unadjusted results to be similar.

**Aim 1. TR+UC is superior to UC alone:** A 6-week program of TR targeting arm movement added to UC will result in better arm function as compared to UC alone. The primary endpoint is the change in ARAT score from baseline to 1 month after end of therapy (Visit 4).

The mean differences in ARAT score change from Visit 1 (baseline) to Visit 4 (1 month after end of therapy) will be compared on the log scale using an inverse propensity adjusted t test. A similar method will be used for the secondary change from Visit 1 to Visit 3 (end of therapy). We will first compare the combined TR + UC groups versus the UC group (Aim 1) and then compare TR+Sinemet+UC versus TR+placebo+UC under this model. (Aim 2). As a secondary analysis, we will report the corresponding unadjusted results.

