The difference in ARAT score change between [1] the combined TR group and [2] the UC group will be computed and the distributions compared using ANCOVA, adjusting for Visit 1 ARAT score and propensity score. Specifically, this Aim will compare UC vs. the combined two TR groups (TR+Sinemet plus TR+placebo).

Exploratory analyses will examine whether aphasia or neglect affect TR efficacy by determining if the extent of aphasia (Visit 1 LAST score) or neglect (Visit 1 SCT score), respectively, is correlated with change in ARAT score from Visit 1 to Visit 4. We will use a linear regression model with ARAT change as the outcome, and with treatment group, LAST score, and propensity score as predictors in order to assess the association. This will be repeated using SCT score instead of LAST score. Restricted cubic splines will be used to determine whether the relationships of language screening and neglect to ARAT score change are each linear.

An additional exploratory analysis will examine whether results vary according to the actual TR dose (the total number of arm repetitions across the 36 treatment sessions), using similar regression methods. Sex will also be explored: while females may have poorer functional outcomes after stroke, it is unclear whether the same underlying factors predict that sex will also be associated with a poorer response to rehabilitation therapy.

Analyses will be repeated examining a secondary endpoint, BBT, and then using several tertiary endpoints (FMA-UE, CES-D, mRS, NHPT, SIS-ADL, and SIS-hand). The lead secondary endpoint is the BBT, and this will be analyzed using alpha=0.05. The tertiary endpoints are considered exploratory and will be examined without correction for multiple comparisons. The same statistical methods as above will be used except that the dependent measure will be change from Visit 1 to Visit 4 in each of the secondary/tertiary endpoints. An additional analysis will examine mRS as the dependent variable but instead using a shift analysis (ordinal logistic repeated measures regression) of mRS change score from Visit 1 to Visits 3 and 4.

To aid in the interpretation of the above analyses, additional corollary analyses will repeat above but use as the dependent measure change from Visit 1 to Visit 3. This will be done for the ARAT as well as for the FMA-UE, BBT, mRS, and SIS-hand subsection.

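### The stated 80% power for Aim 1 makes no allowance for the stated dropout: with 72 enrolled, an unadjusted comparison of completers has about 75% power at 10% dropout and 70% at the 20% maximum

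*Combined protocol and SAP*

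**What the plan says.** The Sample Size section powers the study for Aim 1 only, pooled telerehabilitation (TR) against usual care (UC). At a two-sided alpha of 0.05 and an SD of 7.4, it states that "this study will have 80% power to detect a mean difference between groups of 5.7 points" in ARAT change, "with a total of 72 patients: 27 in TR+Sinemet, 27 in TR+placebo, and 18 in UC". It gives 5.7 points as the MCID. It then says: "The study is funded to enroll 72 patients. Subject dropout may be as high as 20%, and so when possible additional patients may be enrolled". It gives no inflated target, no number of extra patients and no power after dropout.

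The Statistical Analysis section sets the primary population as intent-to-treat, "consisting of all randomized subjects and multiple imputation for missing data". For Aim 1 the mean changes from Visit 1 to Visit 4 "will be compared on the log scale using an inverse propensity adjusted t test". A later paragraph describes distributions "compared using ANCOVA, adjusting for Visit 1 ARAT score and propensity score". Unadjusted results are secondary: "The corresponding unadjusted changes will also be reported as a secondary analysis". ARAT is also collected at Visit 3. No imputation model is given.

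**The concern.** The number 72 plays two roles: it is the count that yields 80% power, and it is the count the study is funded to enrol. Both hold together only if nobody is lost, yet the next sentence allows for losing up to a fifth. The only response offered is extra enrolment that is conditional, unquantified and outside the funded number.

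Aim 1 is the one comparison the study is sized for, and 5.7 points is the effect it is meant to detect. Someone reading a null result would take the chance of missing a true 5.7-point difference to be 20%. On the basis used for sizing, at the plan's own dropout ceiling, that chance is about 30%. UC has only 18 patients, so losses concentrated there cost more than equal losses.

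**Working it through.** **Inputs from the Sample Size section.** Difference 5.7; SD 7.4; two-sided alpha 0.05; 54 TR (27 + 27) against 18 UC; 72 funded; dropout up to 20%. The 10% case and the other intermediate rates are illustrative and not in the documents. Dropout is read as a missing Visit 4 ARAT.

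**Formula.** Two-sample t test, power from the noncentral t distribution with n1 + n2 − 2 degrees of freedom and noncentrality 5.7 / [7.4 × √(1/n1 + 1/n2)].

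**Reproducing the stated figure.** With 54 and 18: √(1/54 + 1/18) = 0.2722; 7.4 × 0.2722 = 2.014; 5.7 / 2.014 = 2.830. Power is 79.7% (normal approximation 80.8%). The plan's 80% is confirmed, with all 72 evaluable.

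**Applying dropout.** Both groups are multiplied by (1 − d), with 72 enrolled.

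| Dropout | TR vs UC with data | Noncentrality | Power | Difference detectable at 80% power |
|---|---|---|---|---|
| 0% | 54 vs 18 | 2.83 | 79.7% | 5.7 |
| 5% | 51.3 vs 17.1 | 2.76 | 77.6% | 5.9 |
| 10% | 48.6 vs 16.2 | 2.68 | 75.3% | 6.0 |
| 15% | 45.9 vs 15.3 | 2.61 | 72.8% | 6.2 |
| 20% | 43.2 vs 14.4 | 2.53 | 70.1% | 6.4 |

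Whole-patient counts agree: 51 vs 17 gives 77.3%, 43 vs 14 gives 69.1%, 43 vs 15 gives 71.4%.

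**Uneven loss, as illustration only.** Losing 14 patients, power is about 59% if 8 come from UC (48 vs 10) and about 76% if all come from TR (40 vs 18). Nothing in the plan predicts either pattern.

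**Enrolment that would keep 72 evaluable.** 72 / 0.9 = 80 at 10% dropout; 72 / 0.8 = 90 at 20%.

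**What imputation and adjustment might recover.** The documents give no correlation or variance explained for ARAT, so everything in this step is assumed. For imputation from Visit 3 ARAT, take the effective share of the sample as (1 − d) + d × h × ρ², where h is the fraction of dropouts with Visit 3 data (0.5 to 1) and ρ the Visit 3 to Visit 4 correlation (0.5 to 0.9). At d = 0.2 the share runs from 0.8 + 0.2 × 0.5 × 0.25 = 0.825 to 0.8 + 0.2 × 1 × 0.81 = 0.962. For baseline adjustment, the residual SD is 7.4 × √(1 − R²), with one degree of freedom lost: 7.02 for R² = 0.10 and 6.72 for R² = 0.176.

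| Assumed recovery | Power at 20% dropout | Power at 10% dropout |
|---|---|---|
| Imputation only | 71–78% | 76–79% |
| R² = 0.10 only | 75% | 80% |
| R² = 0.176 only | 78% | 83% |
| Imputation and R² = 0.10 | 76–82% | 80–83% |
| Imputation and R² = 0.176 | 79–85% | 83–86% |

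The two gains may overlap if the imputation also uses baseline data. The 0.176 is a weak benchmark. The Background reports it for TR patients in the prior national trial after screening 43 baseline measures; that trial's primary endpoint was FMA-UE, and the figure is not variance explained by Visit 1 ARAT.

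**The case against.** The strongest reply is that the plan contains no miscalculation. Its 80% is correct for 72 patients, dropout is disclosed in the next sentence, and a response is offered. That is true. The criticism is that the 80% carries no dropout allowance, not that dropout is ignored. The response has no number and lies beyond the funded enrolment, so a reader cannot count on it.

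A second reply is that 75% and 70% belong to an analysis the plan does not make primary. The primary analysis keeps all randomised patients through multiple imputation, weights by propensity and works on the log scale; nowhere is the unadjusted secondary analysis called completers-only. This also stands, and it is why the figures are confined to the raw-scale comparison on which the study was sized. Imputation keeps patients in the analysis but restores only the information that observed data carry about the missing values. Across the range assumed here, imputation alone does not bring power back to 80%. Combined with baseline adjustment it might, but the plan claims no such gain, and it is not clear that the ANCOVA is the primary model.

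Third, 20% is a ceiling, and stopping therapy need not mean losing the endpoint. Home assessment is allowed at Visits 3 and 4, and UC patients are offered TR after Visit 4 to aid retention. The real shortfall may therefore be small. Even so, the Sample Size section itself ties dropout to a need for more patients, which supports reading it as lost evaluable patients.

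**Conclusion.** The concern holds. The stated 80% is right only with about 72 patients providing Visit 4 ARAT, and the plan funds 72 enrolled while allowing for up to 20% loss. For an unadjusted raw-scale comparison of completers with equal dropout, power is about 75% at 10% and 70% at 20%; at 20% the difference detectable with 80% power rises from 5.7 to about 6.4 points.

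This rests on dropout meaning a missing Visit 4 ARAT, on nothing being recovered by imputation or adjustment, and on no extra patients being enrolled. It says nothing firm about the primary analysis, whose power the documents do not allow one to derive. The loss is gradual and moderate, but the power statement should be corrected because Aim 1 depends on it.

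**What to change.** Replace the power and dropout statements in the Sample Size section with text to this effect:

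> Eighty percent power for a 5.7-point difference requires 72 patients with Visit 4 ARAT. With 72 enrolled, an unadjusted comparison of completers has about 75% power at 10% dropout and about 70% at 20%, where 80% power is reached for a difference of 6.4 points.

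If credit is to be taken for imputation or covariate adjustment, name the variables used and give the assumed correlation or R² as a labelled assumption. State what the conditional extra enrolment amounts to: a number (80 enrolled keeps 72 evaluable at 10% dropout, 90 at 20%), or that none is planned.

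The cost is one paragraph and a less favourable stated power. Enrolment, conduct and analysis need not change.

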### Statistical Analysis

We will present descriptive statistics by group for the important covariates including age, site, time from stroke to randomization, MEP status, and hours of outside rehabilitation. We will also report compliance, defined as the percentage of the 36 sessions during which patients complete more than half ( $\geq 36$  min) of assigned activities. For all analyses, data not normally distributed will be appropriately transformed.

Primary efficacy analysis will use the Intent-To-Treat population, consisting of all randomized subjects and multiple imputation for missing data. Secondary analysis will examine the Per-Protocol population, defined as all subjects with complete data who complete  $\geq 36$  minutes of assigned activities on  $\geq 30$  of the 36 therapy sessions over no more than 8 weeks. Analyses will be performed using SAS and R software.

Logistic regression will be used to create a propensity score for treatment group using age, time from stroke to randomization, and total hours of outside rehabilitation therapy from Visit 1 to Visit 4 (or Visit 3 when change is to visit 3). Inverse weights based on this score will be used in secondary analyses to compute adjusted change distributions and corresponding p values. The primary analyses will be based on the inverse propensity score weighted (adjusted) change from base. The corresponding unadjusted changes will also be reported as a secondary analysis. Since this is a randomized trial, we expected the primary propensity adjusted and unadjusted results to be similar.

**Aim 1. TR+UC is superior to UC alone:** A 6-week program of TR targeting arm movement added to UC will result in better arm function as compared to UC alone. The primary endpoint is the change in ARAT score from baseline to 1 month after end of therapy (Visit 4).

The mean differences in ARAT score change from Visit 1 (baseline) to Visit 4 (1 month after end of therapy) will be compared on the log scale using an inverse propensity adjusted t test. A similar method will be used for the secondary change from Visit 1 to Visit 3 (end of therapy). We will first compare the combined TR + UC groups versus the UC group (Aim 1) and then compare TR+Sinemet+UC versus TR+placebo+UC under this model. (Aim 2). As a secondary analysis, we will report the corresponding unadjusted results.

The difference in ARAT score change between [1] the combined TR group and [2] the UC group will be computed and the distributions compared using ANCOVA, adjusting for Visit 1 ARAT score and propensity score. Specifically, this Aim will compare UC vs. the combined two TR groups (TR+Sinemet plus TR+placebo).

Exploratory analyses will examine whether aphasia or neglect affect TR efficacy by determining if the extent of aphasia (Visit 1 LAST score) or neglect (Visit 1 SCT score), respectively, is correlated with change in ARAT score from Visit 1 to Visit 4. We will use a linear regression model with ARAT change as the outcome, and with treatment group, LAST score, and propensity score as predictors in order to assess the association. This will be repeated using SCT score instead of LAST score. Restricted cubic splines will be used to determine whether the relationships of language screening and neglect to ARAT score change are each linear.

An additional exploratory analysis will examine whether results vary according to the actual TR dose (the total number of arm repetitions across the 36 treatment sessions), using similar regression methods. Sex will also be explored: while females may have poorer functional outcomes after stroke, it is unclear whether the same underlying factors predict that sex will also be associated with a poorer response to rehabilitation therapy.

Analyses will be repeated examining a secondary endpoint, BBT, and then using several tertiary endpoints (FMA-UE, CES-D, mRS, NHPT, SIS-ADL, and SIS-hand). The lead secondary endpoint is the BBT, and this will be analyzed using alpha=0.05. The tertiary endpoints are considered exploratory and will be examined without correction for multiple comparisons. The same statistical methods as above will be used except that the dependent measure will be change from Visit 1 to Visit 4 in each of the secondary/tertiary endpoints. An additional analysis will examine mRS as the dependent variable but instead using a shift analysis (ordinal logistic repeated measures regression) of mRS change score from Visit 1 to Visits 3 and 4.

To aid in the interpretation of the above analyses, additional corollary analyses will repeat above but use as the dependent measure change from Visit 1 to Visit 3. This will be done for the ARAT as well as for the FMA-UE, BBT, mRS, and SIS-hand subsection.

**Aim 2. TR+Sinemet is superior to TR+placebo:** Among patients randomized to TR, gains in arm function will be greater in those who take Sinemet (25/100) prior to daily TR, as compared to patients who take placebo prior to TR.

The above analyses will be repeated but instead comparing patients randomized to [1] TR+Sinemet vs. [2] TR+placebo.

**Aim 3. Less CST injury and higher dopamine polygene score predict better recovery of arm function:** Across all subjects, change in arm function will be highest in those with lower % CST injury and in those with higher dopamine polygene scores. These relationships will remain significant when examining only patients randomized to TR. The drug X gene score interaction term will be significant such that the slope of arm gains in relation to the polygene score will be smaller (less steep) in those receiving Sinemet.

**H3A:** Using linear regression, we will test whether lower % CST injury predicts higher change in ARAT score from Visit 1 to Visit 4, after controlling for baseline ARAT score and clinical measures (age, time from stroke to randomization, and total hours of outside rehabilitation therapy from Visit 1 to Visit 4). Primary analysis will examine all enrollees. Secondary analysis will examine this relationship separately for patients randomized to one of the two TR groups, while tertiary analysis will examine this separately across all three treatment groups.

Restricted cubic splines will be used to determine if the effect of continuous covariates such as age are linear. A linear model that includes individual clinical measures will be used rather than propensity adjustment so that the effect of % CST injury can be compared to the effects of the other covariates. This approach also allows us to test the hypothesis that % CST injury predicts ARAT gains beyond what can be learned from clinical variables alone.

**H3B:** We will test whether higher dopamine polygene score predicts higher change in ARAT score from Visit 1 to Visit 4, after controlling for the same covariates as in H3A. Analyses will follow those described in H3A.

Secondary analysis will repeat H3A and H3B using change in BBT from Visit 1 to Visit 4 as the dependent measure. Tertiary analyses will repeat these methods focusing on change in FMA-UE, CES-D, mRS, NHPT, SIS-ADL, and SIS-hand scores.

An additional H3B analysis will examine the drug X gene score interaction term in those patients randomized to TR (i.e., TR+Sinemet or TR+placebo). Based on our prior findings in healthy subjects, this term is hypothesized to be significant such that the slope of ARAT change in relation to the polygene score will be smaller (less steep) in those receiving Sinemet.

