### Baseline Assessments

Additional assessments will be completed during Visit 1 in order to more fully characterize the patient's functional status at baseline:

- **Fugl-Meyer Arm Motor Assessment for the upper extremity (FMA-UE)**
- **Modified Rankin Scale (mRS)**, scoring both
  - pre-stroke mRS
  - current mRS
- **Shoulder Abduction Finger Extension (SAFE) Score**
- **Handedness Inventory** (pre-stroke)
- **Star Cancellation Test (SCT)**
- **The Language Screening Test (LAST)**
- **Nine Hole Peg Test (NHPT)**
- **Optimization in Primary and Secondary Control (OPS) Scale**
- **Physical Activity Enjoyment Scale (PACES)**
- **Screening question for Restless Legs Syndrome**
- **Reaction Time Test**
- **Modified Ashworth Scale (mAS)**
  - paretic pectoralis major
  - paretic biceps brachii

Dopaminergic enhancement of rehabilitation therapy early after stroke (TR-Dopa)  
Protocol\_20230721

All Visit 1 assessments are available in a single “Visit 1” packet, located in the lab’s Box folder. Details regarding administration of each assessment is found within individual CRFs. The Visit 1 folder on Box also includes a handout for TR input devices, which can be given to patients for reference. Visit 1 may be broken into more than one session, as needed.

After all assessments have been completed, provide an overview of how to access and use the TR system for daily arm motor training.

Note that all study visits may be broken into more than one visit to the lab for any patient who requests this (e.g., due to time constraints).

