## TR System Overview

Patients will be participating in daily (6 days/week) TR training over the course of 6 weeks (up to 8 weeks is permitted to complete 36 sessions). If an enrollee is an inpatient at Cal Rehab at the time of enrollment, guidance for use of the TR system will be at the end of Visit 1 and at subsequent inpatient TR sessions. If the enrollee is an outpatient referred into the study, guidance for TR use will occur at Visit 1 and at the time that the TR system is delivered to the patient's home. TR guidance will provide an understanding of the general TR layout, the nature of the functional games and exercises used for arm training, other modules such as education and assessment, how to respond to instructions (which are presented verbally and non-verbally as a TR system feature), and how to use each TR input device.

## Visit 2

Visit 2 will be conducted on the UCLA campus. At Visit 2, the patient will undergo an MRI scan of the brain to acquire structural and functional brain images. Pulse sequences will include T1-weighted, T2-weighted, resting state BOLD T2\*, and diffusion tensor imaging. These data will be used to test MRI-based biomarker hypotheses (Aim 3). At this visit, the patient will also be asked about any interval medical history and AEs.

Note: The timing of the MRI may be modified per PI judgment.

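### H3A claims that CST injury predicts beyond clinical variables, but the Visit 1 SAFE score is collected and left out of the comparison; separately, MEP status is listed without a source

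*Combined protocol and SAP*

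**What the plan says.** In the Statistical Analysis section, H3A is a linear regression of ARAT change from Visit 1 to Visit 4 on % CST injury, "after controlling for baseline ARAT score and clinical measures (age, time from stroke to randomization, and total hours of outside rehabilitation therapy"; the therapy hours are counted from Visit 1 to Visit 4. The plan enters these covariates individually instead of using a propensity score. One reason it gives is that this lets it "test the hypothesis that % CST injury predicts ARAT gains beyond what can be learned from clinical variables alone".

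The Visit 1 baseline assessments include the "Shoulder Abduction Finger Extension (SAFE) Score" and the FMA-UE. The Schedule of Events shows SAFE once, at baseline. SAFE is not mentioned in the Statistical Analysis section, and FMA-UE appears there only as an outcome.

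The same section opens with the covariates to be described by group: "important covariates including age, site, time from stroke to randomization, MEP status, and hours of outside rehabilitation". This is the only mention of MEP status in the document, and the abbreviation is not defined. It is read here as motor evoked potential.

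**The concern.** A statement that an imaging marker adds to clinical information is only as strong as the clinical information in the comparison model. Here that side has four covariates:

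- **Time from stroke** is limited by eligibility to 30 days or less, apart from waivers, so it has little room to vary.
- **Outside-therapy hours** build up during follow-up. They cannot be part of what a clinician knows at baseline, yet the Study Overview says the biomarkers should identify responders prospectively.
- **Baseline ARAT and age** are therefore the main baseline comparators. ARAT itself is restricted at entry to scores below 32 of 57.

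A bedside arm-motor score taken at Visit 1 is left out. If SAFE carries some of the same information as % CST injury, a significant CST term in the planned model could partly reflect what SAFE already shows without a scan. What is at stake is the wording of one Aim 3 conclusion. Aims 1 and 2 are not affected.

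The MEP item is a smaller matter: the plan promises a descriptive table entry that no described procedure would fill.

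**Working it through.** **The plan's own figure.** The only design calculation is for Aim 1 (Sample Size): 54 TR against 18 UC, difference 5.7, SD 7.4, two-sided alpha 0.05. The standardised difference is 5.7 / (7.4 × √(1/54 + 1/18)) = 5.7 / 2.014 = 2.83. Normal-theory power is then Φ(2.83 − 1.96) = 0.808, or 0.797 by noncentral t on 70 degrees of freedom. The stated 80% is reproduced. It has no bearing on H3A, for which the plan gives no power figure.

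**Procedures against analyses.**

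- SAFE: collected at Visit 1 (Baseline Assessments, Schedule of Events); used in no analysis.
- MEP status: named once, for description only. It is absent from the screening list, the Visit 1 list, the TR-based weekly assessments and Visits 3 to 5. At Visit 2, "the patient will undergo an MRI scan of the brain to acquire structural and functional brain images", with no stimulation procedure. The propensity score uses age, time from stroke and outside-therapy hours. The ANCOVA adds baseline ARAT. MEP status is in none of these models, nor in H3A or H3B.

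**Cost of adding SAFE.** The planned H3A model has 5 predictors (% CST injury plus four covariates), before any spline terms. Residual degrees of freedom are 72 − 5 − 1 = 66, or 65 with SAFE. At 20% dropout, 72 × 0.8 = 57.6, about 58 patients, giving 52 and 51. MRI-ineligible enrollees would lower these numbers further.

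Power for one coefficient comes from a noncentral F with 1 and N − k − 1 degrees of freedom and noncentrality N × R²/(1 − R²), where R² is the partial R-squared of CST injury and k the number of predictors. The Background reports 17–33% of variance explained in earlier studies but does not say that this is covariate-adjusted. Taking 0.17 as a partial R-squared is therefore an assumption.

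| Partial R² of CST | N | Noncentrality | Power, 5 predictors | Power, 6 predictors |
|---|---|---|---|---|
| 0.17 | 72 | 14.75 | 0.966 | 0.966 |
| 0.17 | 58 | 11.88 | 0.923 | 0.922 |
| 0.085 (half absorbed by SAFE) | 72 | 6.69 | 0.722 | 0.722 |
| 0.085 (half absorbed by SAFE) | 58 | 5.39 | 0.625 | 0.625 |

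The lost degree of freedom is negligible. Any loss of power would come from real overlap between SAFE and CST injury, which is what the claim has to withstand.

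**What omission could do (illustration only).** Assume, as a worst case, that CST injury has no effect beyond SAFE. Let SAFE have partial R-squared s with ARAT change after the listed covariates, and let ρ be its partial correlation with CST injury. With SAFE omitted, CST injury shows an apparent partial R-squared of ρ² × s. For s = 0.20 and ρ = 0.5 this is 0.05. At N = 72 the noncentrality is 72 × 0.05/0.95 = 3.79, and the chance of a significant CST term is 0.483. For s from 0.10 to 0.30 and ρ from 0.3 to 0.7 in absolute value, the chance runs from 0.125 to 0.935 at N = 72 and from 0.110 to 0.873 at N = 58, against a nominal 0.05. Neither s nor ρ is in the documents.

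**The case against.** The strongest reply is that H3A is not short of a motor measure. It already adjusts for baseline ARAT, a 57-point arm scale. The Background also gives reasons for expecting little from clinical variables: a model built after screening 43 baseline measures explained only 17.6% of variance, and in five studies % CST injury was a better predictor than baseline behavioural status. Collecting a score does not oblige the plan to model it, and the same argument could admit FMA-UE, BBT or NHPT.

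Much of this stands. ARAT covers part of the ground, and adding SAFE is a check on the claim rather than a repair of an invalid test. However, the Background results come from other populations and do not show what CST injury adds once SAFE is known. In H3A the phrase "CST injury predicts ARAT gains beyond what can be learned from clinical variables alone" still rests on four covariates, one of them measured after baseline.

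A reader might also infer more than the documents support:

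- **That the missing MEP data break an analysis, or leave the arms without a baseline motor comparison.** They do not. MEP status is for description only, and ARAT, BBT, FMA-UE, SAFE, NHPT and % CST injury can all be shown by arm.
- **That MEP status will certainly be missing for every patient.** The top of the schedule table is not legible in the public copy, so an entry there cannot be excluded.
- **That SAFE can stand in for MEP status, or is the bedside sign closest to corticospinal output.** The documents give only SAFE's name and visit.
- **That a known share of the CST effect is not incremental.** The illustration assumes the overlap, and its width shows that the size cannot be derived.

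**Conclusion.** The point holds as a mismatch between claim and model. H3A can show that % CST injury predicts ARAT gains beyond four named covariates. It cannot, as specified, support a statement about clinical variables in general while a motor score collected at Visit 1 is left out. The consequence is confined to the interpretation of Aim 3; the sample size of 72 and the Aim 1 test are unchanged. How far SAFE would reduce the CST increment depends on correlations that the documents do not give, and the reduction could be anything from none to substantial.

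The MEP item is a minor correction with no effect on any specified test. It rests on reading the abbreviation as motor evoked potential and on the procedure lists that can be read.

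**What to change.** In the Statistical Analysis section, under H3A:

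1. Keep the planned model unchanged.
2. Prespecify a second model that adds the Visit 1 SAFE score to all the listed covariates, including outside-therapy hours, so that the two models differ only by SAFE. Fit both to the same patients.
3. Report the added R-squared of % CST injury in both models.
4. State in advance that the claim of prediction beyond clinical variables will be made only if the CST term holds with SAFE included. Otherwise, limit the claim to the covariates named.

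In the list of covariates to be described by group, state when and how MEP status is obtained, or delete it. Report SAFE by group under its own name, not as a substitute for MEP status.

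The cost is SAP wording only, on data already collected. The downsides are one degree of freedom, some collinearity of SAFE with baseline ARAT (which widens the interval for each), and a CST increment that may look smaller.
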